6.1 SOA Table: Schedule 1 Dose Escalation of SL-279252

Dosing Schedule 1		D1, D8, D15 in cycle 1 over 28 days, thereafter every 2 weeks (D1, D15) over 28 days														Post Tx ^f	Follow up ^s	
Cycle Length = 28 days		Cycle 1							Cycle 2				Cycle 3		≥ Cycle 4			
Procedures/Assessments ^b	Screen ^a	D1				D8	D15		D22	D1	D2	D15	D16	D1	D15	D1	D15	
	Study Days -21 to -1	1	2	3, 4	5	8	15	16	22	29	30	43	44	57	71	85 etc.	99 etc.	w/in 30 d
Informed consent	X																	
Inclusion/exclusion criteria ^c	X	X																
Demographics & medical history	X																	
Cancer treatment history	X																	
Physical examination	X	X				X	X			X				X		X	X	
Pulse oximetry ^d	X	X ^{d1}	X ^d ₂	X ^{d2}	X ^{d1}	X ^{d1}	X ^{d2}	X	X ^{d1}	X ^{d2}	X ^{d3}		X ^{d3}	X ^{d3}	X ^{d3}	X ^{d3}	X	
Vital signs ^d	X	X ^{d1}	X ^d ₂	X ^{d2}	X ^{d2}	X ^{d1}	X ^{d1}	X	X ^{d1}	X ^{d2}	X ^{d3}		X ^{d3}	X ^{d3}	X ^{d3}	X ^{d3}	X	
Height	X																	
Weight	X	X					X			X		X		X	X	X	X	
ECOG performance status	X	X				X	X			X				X		X	X	
Pregnancy test ^e	X		Every 8 weeks											X	Every 8 weeks		X	
Hematology profile ^f	X	X	X			X	X	X	X	X	X	X	X	X	X	X	X	X
Chemistry profile ^f	X	X	X			X	X	X	X	X	X	X	X	X	X	X	X	X
Ferritin	X																	
Coagulation profile ^g	X	X	X			X	X	X	X	X	X	X	X					
Thyroid test ^h	X									X				X		X ^h		X
Antiviral testing (HBV/HCV) ⁱ	X																	
Cardiac:12-Lead ECG/ECHO ^j	X																	
Tumor imaging ^k	X		Every 8 weeks through week 24 (see footnote k)											X	(see footnote k)		X	X
PK/immunogenicity/ cytokine sample(s) in dose escalation cohorts ^L		X	X	X	X	X	X		X	X				X		X		X
Complement ^m		X	X			X	X			X	X							
Immunophenotyping ^m		X	X		X	X	X	X		X	X	X	X					
Receptor Occupancy ^m		X	X			X	X			X	X	X	X					
SL-279252 administration ⁿ		X			X	X			X		X			X	X	X	X	
Concomitant medications	X	X	Continuous Monitoring														X	
AEs/SAEs ^o	X	X	Continuous Monitoring: Collect Ad hoc sample of clinical safety labs if IRR or CRS event occurs as outlined in Section 6.6.1														X	
Archival tumor tissue ^p	X																	

Dosing Schedule 1		D1, D8, D15 in cycle 1 over 28 days, thereafter every 2 weeks (D1, D15) over 28 days														Post Txt ^r	Follow up ^s	
Cycle Length = 28 days		Cycle 1							Cycle 2				Cycle 3		≥ Cycle 4			
Procedures/Assessments ^b	Screen ^a	D1				D8	D15		D22	D1	D2	D15	D16	D1	D15	D1	D15	
	Study Days -21 to -1	1	2	3, 4	5	8	15	16	22	29	30	43	44	57	71	85 etc.	99 etc.	w/in 30 d

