k. **Tumor Assessment:** Tumor assessments are required for all subjects within 28 days prior to enrollment. Baseline and on-treatment tumor assessments for solid tumors by iRECIST should include CT with contrast of chest, abdomen, and pelvis and other known sites of disease at each time point. Bone scan and positron emission tomography (PET)/CT should be performed only if clinically indicated. Baseline and on-treatment tumor assessment for lymphoma by RECIL 2017 should be done using CT scan with contrast and PET/CT of neck, chest, abdomen, and pelvis and other known sites of disease at each time point. Please refer to Section 8 for requirements regarding disease assessment. Tumor assessments must be performed at screening and at the following intervals until disease progression is confirmed: approximately every 8 weeks through week 24 (e.g., C3D1, C5D1, C7D1), every 12 weeks up to year 2 (prior to cycles 10, 13, 16, 19, 22, 25, 28 and 31), and then every 6 months (prior to cycles 37, cycle 43, etc.) up to conclusion of the study. Confirmatory scans should be performed at least 4 weeks (>28 days), but no longer than 8 weeks after initial documentation of an objective response. Subjects who discontinue study treatment for reasons other than disease progression (e.g., AE or withdrawal of consent) will be monitored for radiologic response until start of another anti-cancer therapy, or disease progression, withdrawal of consent or death.

l. **PK/immunogenicity (i.e., ADA) and cytokine sampling (Dose Escalation Cohorts):** PK, ADA, and cytokine time points for collection of samples are outlined in supplementary tables in Section 6.1.1. ([Table 6](#), [Table 7](#) and [Table 8](#)). Blood volumes required are provided in the SLM. PK, ADA, cytokine samples should not be collected from infusion port for drug delivery i.e., recommend having a separate line in the opposite arm for sample collection. If subject has positive ADA test on D1 of cycle 13, then follow up predose samples for PK/ADA should be collected every ~90 days on D1 of subsequent treatment cycles until ADA resolves to baseline. If ADA positivity is detected within 7-30 days after the last dose of SL-279252, then follow up testing for PK/ADA should be performed at monthly intervals until ADA resolves to baseline.

m. **Correlative laboratory studies:** Refer to supplementary [Table 9](#) for details in Section 6.1.2 plus see the SLM for amount of blood needed.

- *Complement*

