## 8. EFFICACY ANALYSES

The efficacy analysis will be based on the All Treated population and/or Efficacy Evaluable population, as appropriate. The efficacy endpoints include ORR, CBR, time to response (TTR), DOR, tumor size change from baseline for target lesions, PFS, and OS.

Response assessment will be based on the iRECIST for solid tumors and RECIL 2017 for lymphoma. Radiographic disease assessment must be performed at screening, and at the following intervals until a disease progression is confirmed: every 8 weeks through week 24, every 12 weeks

up to year 2 and then every 6 months up to conclusion of the study. Disease assessment window is +/- 1 week. Confirmatory assessments should be performed at least 4 weeks ( $\geq$  28 days) after the initial documentation of an objective response or an unconfirmed disease progression. Subjects who discontinue study treatment for reasons other than disease progression will be monitored for radiologic response until start of new anti-cancer therapy, disease progression, withdrawal of consent or death.

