**Table 5. Summary of Censoring Guidelines for PFS based on iRECIST**

Situation	Date of PD/Death or Censoring	PFS Outcome
Documented iCPD or death	Date of the initial iUPD that is confirmed or death, whichever comes first	Event (unless the censoring rule specified below)
iUPD and if iUPD is not confirmed and there is no subsequent iSD, iPR or iCR 	Date of the last iUPD	Event (unless the censoring rule specified below)
Death or iUPD immediately after $\geq 2$ consecutive missed or non-evaluable disease assessments  as per the protocol specified assessment schedule	Date of last evaluable disease assessment prior to missed or non-evaluable assessments, or the first dose of investigational product, whichever occurred last	Censored
No iCPD or death at time of analysis or lost to follow-up	Date of last evaluable disease assessment	Censored
No tumor assessment at baseline OR No tumor assessment post-first dose, and no death prior to second scheduled post-baseline disease assessment	Date of first dose	Censored

 If iUPD is not confirmed and there is no subsequent iSD, iPR or iCR, then the iUPD date should still be used as progression event for PFS in the following scenarios: if the subjects stop study treatment because they were not judged to be clinically stable, or no further response assessments are done; the next timepoint responses are all iUPD, and iCPD never occurs; or the subject dies from their cancer.

 Two or more consecutive assessments is defined as  $\geq 16+1$  weeks for the first 6 months or  $\geq 24+1$  weeks for 6-24 months (two disease assessments as per protocol plus a one week visit window to allow for a late assessment) after the last evaluable post-baseline disease assessment. If a subject has two or more consecutive missed or non-evaluable assessments followed by an assessment showing no radiologic disease progression, then the assumption will be that the subject did not progress during the missed or non-evaluable assessments.

The median and quartiles of PFS and their 95% CIs will be assessed using the Kaplan-Meier method and Brookmeyer and Crowley (1982) method, respectively. The proportion of subjects

that are progression free and alive at 12, 24, 48, 72, 96 weeks and other timepoints of interest and associated 95% CI will be estimated using the Kaplan-Meier method.

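### The two-missed-scans censoring rule for PFS and DOR fails for gaps that span the week-24 change from 8- to 12-weekly scans, and does not say which date selects the 17- or 25-week limit.

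*SAP*

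**What the plan says.** SAP Tables 5 and 6 censor a death or progression that directly follows two or more successive scans missed or not evaluable, judged against the protocol's schedule. Table 5 sets the censoring date as "Date of last evaluable disease assessment prior to missed or non-evaluable assessments, or the first dose of investigational product, whichever occurred last".

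The footnotes turn two missed scans into fixed gaps: at least 16+1 "weeks for the first 6 months or" at least 24+1 "weeks for 6-24 months (two disease assessments as per protocol plus a one week visit window to allow for a late assessment". The gap is counted "after the last evaluable post-baseline disease assessment".

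SAP Section 8 gives the scan schedule as "every 8 weeks through week 24, every 12 weeks" up to year 2, then 6-monthly, with a window of one week either side. Protocol Section 6.1, footnote k, agrees: "approximately every 8 weeks through week 24 (e.g., C3D1, C5D1, C7D1), every 12 weeks up to year 2".

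The rule reaches beyond the two tables. SAP 8.9.3 applies the RECIST 1.1 rule to RECIL PFS, and SAP 8.6 applies the PFS censoring rules to all three versions of DOR.

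**The concern.** The footnotes claim that their week limits equal two protocol scans plus a one-week window. That holds only if the two scans following the last evaluable one are spaced at the interval the limit assumes. Around week 24 they are not. The footnotes also leave open whether the date of the last scan or the date of the event decides between 17 and 25 weeks, so two programmers could each follow the text and produce different PFS data.

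At stake is whether a progression or death is an event or is censored back at the previous scan, 20 or 24 weeks earlier in the on-time examples worked below. The SAP reads Kaplan-Meier PFS proportions at 24 and 48 weeks, which is the stretch affected.

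**Working it through.** **Inputs**
- Scan visits: Protocol 6.1 gives C3D1, C5D1 and C7D1, then "prior to cycles 10, 13, 16, 19, 22, 25, 28 and 31", then cycles 37 and 43, with "Cycle Length = 28 days". Cycle n starts at week 4 × (n − 1). Scans are therefore due at weeks 8, 16, 24, 36, 48, 60, 72, 84, 96, 108, 120, 144 and 168.
- Window: 1 week (SAP Section 8).
- Month conversion: 30.4375 days (SAP 5.2.3). Six months is 6 × 30.4375 = 182.6 days, or 26.1 weeks.

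**The plan's own figures.** Two intervals plus the window: 2 × 8 + 1 = 17 and 2 × 12 + 1 = 25. Both reproduce.

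**Limits from the schedule.** Limit = due week of the second scan after the last evaluable one − week of the last scan + 1.

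| Last evaluable scan | Second scan after it | Limit (weeks) | SAP limit if last-scan date selects |
|---|---|---|---|
| Week 8 | 24 | 24 − 8 + 1 = 17 | 17 |
| Week 16 | 36 | 36 − 16 + 1 = 21 | 17 |
| Week 24 | 48 | 48 − 24 + 1 = 25 | 17 (24 is below 26.1) |
| Weeks 36 to 96 | 24 weeks later | 24 + 1 = 25 | 25 |
| Week 108 | 144 | 144 − 108 + 1 = 37 | none stated |
| Week 120 | 168 | 168 − 120 + 1 = 49 | none stated |

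The 21-week value appears nowhere in the SAP.

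**Reading A: the last-scan date selects the limit.**
- Scan at week 16, only week 24 missed, progression at the on-time week-36 scan. The gap is 36 − 16 = 20, which is at least 17, so PFS is censored at week 16 after one missed scan.
- Scan at week 24, only week 36 missed, progression at the on-time week-48 scan. The gap is 48 − 24 = 24, at least 17, so PFS is censored at week 24 after one missed scan.
- In general, events from week 33 (16 + 17) up to week 37 after a week-16 scan, and from week 41 (24 + 17) up to week 49 after a week-24 scan, are wrongly censored.

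**Reading B: the event date selects the limit.**
- The two progressions above fall after 26.1 weeks, so the limit is 25. Gaps of 20 and 24 are below it, and both are correctly events.
- On-schedule progression after two missed scans is correctly censored: week 8 to 36 is 28 weeks and week 16 to 48 is 32 weeks, both at least 25.
- Scan at week 8, weeks 16 and 24 missed, death at week 30. The gap is 22, below 25, so the death counts as an event after two missed scans.
- In general, deaths or off-schedule progressions from about week 26.1 to before week 33 (8 + 25) after a week-8 scan, and between weeks 37 and 41 (16 + 25) after a week-16 scan, are wrongly counted.

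**Edge of the window.** The rule says at least, so a week-8 scan, a missed week 16, and the week-24 scan done in window at week 25 gives exactly 17 weeks. That is censored after one missed scan under either reading.

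**The case against.** The strongest reply is that the intent is already clear. The table row refers to the protocol's schedule, and the footnote describes its own weeks as two protocol scans. An on-time week-36 progression after one missed scan does not meet that row, and a careful programmer might see this. That stands as evidence of intent, but the footnote is where the term is defined, and its numbers contradict the row.

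It is also fair that the week-24 example needs both the last-scan reading and 6 months taken as 26.1 weeks. If a scan at week 24 is treated as opening the 12-weekly period, the limit is 25 and that example disappears. The week-16 example remains.

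A reader might infer three stronger things that the documents do not support:
- **That the SAP overlooks the change of interval.** It has two limits because the interval changes. What is missing is a rule for gaps that span the change.
- **That PFS is biased upward.** This follows only under Reading A. Under Reading B extra events are kept, which pulls the other way.
- **That on-schedule progressions after two missed scans would be counted.** They are censored under both readings. Only deaths and off-schedule progressions are affected; Protocol Section 8 allows extra scans at the investigator's discretion.

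**Conclusion.** The point holds. At nominal visit times the rule is correct for a gap between weeks 8 and 24 and for last scans at weeks 36 to 96. It is wrong for gaps that cross week 24, and it is silent on which date selects the limit. Each available reading misclassifies some events against the SAP's own test of two missed scans. The footnotes also give no limit after 24 months, when scans become 6-monthly.

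The size is modest. PFS and DOR are exploratory (Protocol Section 2, Table 4), and under Protocol 9.4.3 their Kaplan-Meier summaries are given only if appropriate. The primary safety objectives, ORR and CBR do not use this rule. The documents give no basis for estimating how many subjects would be affected, and none for assuming that skipped scans accompany deterioration. If they do, censoring under Reading A would be informative. The correction is worth making because a stated rule gives wrong answers and is cheap to repair.

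**What to change.** In both footnotes, replace the fixed week limits with a count against the protocol schedule. Suggested wording: an event is censored if it occurs later than one week after the due date of the second scheduled assessment following the last evaluable one, with no evaluable assessment in between.

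At nominal visits this means a gap of more than 17 weeks after a week-8 scan, 21 after week 16, 25 after weeks 24 to 96, 37 after week 108, and 49 after week 120. The same count applies in the 6-monthly period and to off-schedule last scans. State that a last scan taken within its one-week window is treated as its nominal visit. Using later than, rather than at least, keeps a scan done at the end of its window from being censored after one missed visit.

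The cost is an edit to two footnotes and a few lines of programming before database freeze. RECIL PFS and DOR inherit the change through their existing cross-references.

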#### 8.9.2 PFS based on RECIST 1.1 for solid tumors

PFS based on RECIST 1.1 is defined as time from the first day of treatment to the first documented disease progression (confirmed or not) or death, whichever occurs first. Subjects who have not progressed at the time of analysis will be censored at the time of the latest date of assessment from their last evaluable RECIST assessment. The censoring guidance and the date of PD/death or censoring are given in the Table 6 below.

**Table 6. Summary of Censoring Guidelines for PFS based on RECIST1.1**

Situation	Date of PD/Death or Censoring	PFS Outcome
Documented PD or death	Date of the first PD or death, whichever comes first	Event (unless the censoring rule specified below)
Death or PD immediately after $\geq 2$ consecutive missed or non-evaluable disease assessments  as per the protocol specified assessment schedule	Date of last evaluable disease assessment prior to missed or non-evaluable assessments, or the first dose of investigational product, whichever occurred last	Censored
No PD or death at time of analysis or lost to follow-up	Date of last evaluable disease assessment	Censored
No tumor assessment at baseline OR No tumor assessment post-first dose, and no death prior to second scheduled post-baseline disease assessment	Date of first dose	Censored

 Two or more consecutive assessments is defined as  $\geq 16+1$  weeks for the first 6 months or  $\geq 24+1$  weeks for 6-24 months (two disease assessments as per protocol plus a one week visit window to allow for a late assessment) after the last evaluable post-baseline disease assessment. If a subject has two or more consecutive missed or non-evaluable assessments followed by an assessment showing no radiologic disease progression, then the assumption will be that the subject did not progress during the missed or non-evaluable assessments.

The median and quartiles of PFS and their 95% CIs will be assessed using the Kaplan-Meier method and Brookmeyer and Crowley (1982) method, respectively. The proportion of subjects that are progression free and alive at 12, 24, 48, 72, 96 weeks and other timepoints of interest and associated 95% CI will be estimated using the Kaplan-Meier method.

#### 8.9.3 PFS based on RECIL 2017 for Lymphoma

PFS based on RECIL 2017 is defined as time from the first day of treatment to the first documented disease progression (confirmed or not) or death, whichever occurs first. Subjects who have not progressed at the time of analysis will be censored at the time of the latest date of assessment from their last evaluable RECIL assessment. The censoring guidance and the date of PD/death or censoring are the same as that for PFS based on RECIST 1.1.

If data warrants, the median and quartiles of PFS and their 95% CIs will be assessed using the Kaplan-Meier method and Brookmeyer and Crowley (1982) method, respectively. The proportion of subjects that are progression free and alive at 12, 24, 48, 72, 96 weeks and other timepoints of interest and associated 95% CI will be estimated using the Kaplan-Meier method if data warrants.

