
Dose Escalation and Dose Expansion To explore additional measures of anti-tumor activity of SL-279252
	
 Duration of response (DOR): time between first response (iCR or iPR, whichever is recorded first) and date of disease progression) Time to response (TTR): time from the start of treatment with SL-279252 to the first objective tumor response (iCR or iPR, whichever is recorded first) Progression free survival: time from first dose of SL-279252 to progression or death, whichever comes first Overall survival: time from first dose of SL-279252 to death

Dose Escalation and Dose Expansion : To explore relationship between PK/pharmacodynamics and the relationship between PK and clinical activity including tumor growth kinetics
	PK/pharmacodynamics and clinical activity outcomes as described above

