6.10 Assessment of Anti-tumor Activity

Anti-tumor activity will be assessed in solid tumors according to iRECIST, and in lymphoma according to RECIL 2017. Treatment beyond progression is permitted provided the subject meets protocol specified criteria (see Section 8.3). Imaging studies including CT scan, FDG-PET or MRI for disease assessment will be performed at baseline and at the following intervals until disease progression is confirmed: every 8 weeks through week 24, and every 12 weeks thereafter until year 2, and every 6 months until study conclusion. Refer to Section 8 for additional details. All subjects will be followed up for survival unless they withdraw consent.

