8.3 Criteria for Treatment Beyond Initial Progression

Subjects will be permitted to continue IP beyond initial progressive disease provided the subject does not have clinical symptoms of progression, is tolerating IP, and is gaining clinical benefit as assessed by the investigator. The subject must be made aware of the potential benefits and risks of continuing the IP in the setting of progressive disease by providing a separate written informed consent.

The subject may continue to be treated until one of the following criteria is met:

- Confirmed progressive disease (defined in Appendix Section 16.6.3 for solid tumors and Appendix Section 16.7.1 for lymphomas)
- Meets any of the criteria for discontinuation of IP (see Section 3.6)
- Develops clinical symptoms or signs such that the benefit-risk ratio of continuing therapy is no longer justified
- Experiences rapid progressive disease with risk to vital organs or critical anatomical sites requiring urgent medical intervention
- Decline in ECOG PS

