Progressive Disease: $> 20\%$ increase in the sum of longest diameter of target lesions; for small lymph nodes of < 15 mm posttherapy, minimum absolute increase of 5 mm and long diameter > 15 mm; appearance of new lesion; any FDG-PET finding; any bone marrow involvement; new or no new lesions.

Progressive Disease After Initial Response: after initial response, and in the absence of appearance of new lesions, progressive disease is defined as an increase of the nadir sum of diameters by $> 20\%$.

Response Assessment in Participants Receiving Immune-Modulating Agents, Including Checkpoint Inhibitors: to account for potential ‘pseudoprogression,’ immune-related response criteria should be used, requiring confirmation of progressive disease on two consecutive scans at least 4 weeks apart and inclusion of new lesion measurements in the total tumor burden.

Appearance of New Extranodal Lesion: A minimum of 1 cm in largest diameter of new extranodal lesions is required to confirm progressive disease. New smaller but suspicious lesions should be designated as equivocal; if later confirmed (by CT or biopsy) as due to lymphoma, the documented date of disease progression should be the date of identification as equivocal.

Disseminated Disease: The status of nontarget lesions should be accounted for before formulating the final response status. The International Working Group statement provides a recommended approach to response designation involving the best response of target and nontarget lesions.

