### 8.3 ORR Based on RECIL 2017 for Lymphomas

#### 8.3.1 Response assessment based on RECIL 2017

The response assessment at each assessment per RECIL 2017 is as the following:

- Complete Response (CR)
- Partial Response (PR)
- Minor Response (MR)
- Stable Disease (SD)
- Progressive Disease (PD)
- Not evaluable (NE)

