### 8.3.3 Derivation of Best Overall Response based on RECIL 2017

The best overall response is defined as the best overall response among all post-baseline timepoint assessments until the first PD or the last assessment if PD has not been observed. Based on investigator assessment of overall response at all post-baseline assessments, the best overall response will be determined as the following:

- CR > PR > MR > SD > PD > NE
- CR = at least one CR
- PR = at least one PR or better (and not qualifying for CR).
- SD = at least one SD assessment (or better)  $\geq$  49 days after the first dose (and not qualifying for a CR or PR). The minimum interval from the first dose date for the best response of SD is 8 weeks – 7 days to allow for visit windows of  $\pm$  7 days (49 days).
- Clinical deterioration will not be considered as documented disease progression.

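### For lymphoma the SAP ends DOR and PFS, and by its natural reading best response, at a first unconfirmed PD, although the protocol's criteria call for confirmed PD; SAP Section 12 does not declare this

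*SAP*

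**What the plan says.** **Protocol.** Appendix 16.7.1 sets out the RECIL 2017 categories and then adds a rule for immune-modulating agents. To allow for pseudoprogression, "immune-related response criteria should be used", "requiring confirmation of progressive disease on two consecutive scans at least 4 weeks apart". The same sentence requires new-lesion measurements to be included in total tumor burden. Section 8.3, on continuing treatment after a first progression, lists as an end point "Confirmed progressive disease (defined in Appendix Section 16.6.3 for solid tumors and Appendix Section 16.7.1 for lymphomas". Section 6.10 covers solid tumors and lymphoma together and says that imaging "will be performed at baseline and at the following intervals until disease progression is confirmed". The endpoint line in Section 2 is shorter and does not mention confirmation: "Progression free survival: time from first dose of SL-279252 to progression or death, whichever comes first".

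**SAP.** Section 8.3.1 gives RECIL one PD category, with no split into unconfirmed and confirmed. Section 8.3.3 takes the best response among assessments "until the first PD or the last assessment if PD has not been observed". Section 8.9.3 defines lymphoma PFS as time to "first documented disease progression (confirmed or not) or death, whichever occurs first", and Section 8.6 ends lymphoma DOR by the same rule. Section 12 lists two changes from the protocol: the name of the Screened population and the scope of the DLT Evaluable population.

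**The concern.** The protocol adopts a confirmation rule for lymphoma, allows dosing past a first PD under stated conditions, and keeps scanning until progression is confirmed. The SAP's lymphoma derivations then make no use of those later scans. A first PD that the next scan reverses would still fix the subject's best response and PFS date, so a scan that the protocol's criteria do not accept as progression becomes the event.

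ORR is a secondary outcome, and anti-tumor activity feeds the choice of RP2D. PFS, DOR and TTR are exploratory. Dose escalation and the MTD are not touched.

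**Working it through.** No sample size, power or error rate depends on this point, so the check is a comparison of texts followed by an illustration.

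**1. The rules side by side**

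| Item | Solid tumors (SAP) | Lymphoma (SAP) | Lymphoma (Protocol 16.7.1) |
|---|---|---|---|
| PD categories | iUPD and iCPD | one PD category (8.3.1) | PD needs a second consecutive scan |
| Best response stops at | first iCPD (8.1.3); also first PD under RECIST 1.1 (8.2.3) | first PD (8.3.3) | not stated; the criteria require confirmed PD |
| PFS and DOR event | confirmed (8.9.1, 8.6); also unconfirmed under RECIST 1.1 (8.9.2, 8.6) | first PD, confirmed or not (8.9.3, 8.6) | not stated; the criteria require confirmed PD |

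Solid tumors therefore get two versions, one confirmed and one not. Lymphoma gets only the version without confirmation. The introduction to SAP Section 8 itself expects a confirmatory assessment after an unconfirmed progression.

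For PFS and DOR the SAP is explicit. For best response it says only the first PD. Reading that as unconfirmed is an inference from the single category in 8.3.1 and from 8.6 and 8.9.3.

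**2. What the difference does to one subject**

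These subjects are assumed, not taken from the documents. Scans fall on schedule at weeks 8, 16 and 24, which are study days 57, 113 and 169 (2 × 28 + 1, 4 × 28 + 1, 6 × 28 + 1). PD arises from target-lesion growth without new lesions. Months are days / 30.4375 (SAP 5.2.3).

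*Subject A: PD, PR, PR.* The second scan comes 113 − 57 = 56 days after the first, which meets the four-week minimum, and it does not show PD.
- SAP as written: best response PD; not in the ORR numerator; no TTR or DOR; PFS event at 57 / 30.4375 = 1.9 months.
- Confirmed-PD rule: best response PR (SAP 8.3.3 needs only one PR); TTR 113 / 30.4375 = 3.7 months; DOR runs from day 113; PFS censored at 169 / 30.4375 = 5.6 months.

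*Subject B: PR, PD, PR.*
- SAP as written: still a responder, but DOR ends as an event at 113 − 57 + 1 = 57 days (1.9 months), with a PFS event at 3.7 months.
- Confirmed-PD rule: DOR censored at 169 − 57 + 1 = 113 days (3.7 months); PFS censored at 5.6 months.

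*Subject C: PD, PD.* Both rules give best response PD and a PFS event on day 57.

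The rules differ only where a first PD is not upheld by the next scan.

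**3. How far it reaches in the outputs**

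The efficacy tables and figures listed in SAP 14.1 and 14.2 are all for solid tumors. Lymphoma efficacy appears in Listings 16.2.6.6 to 16.2.6.9, 16.2.6.11, 16.2.6.14 and 16.2.6.16. The ORR, DOR and PFS summaries for lymphoma (SAP 8.3.2, 8.6, 8.9.3) are conditional on enough data. The response at each visit is listed beside the derived best response (SAP 8.3.2).

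**The case against.** The protocol is not uniform on this. Its endpoint definitions say only progression. Its lymphoma response table (16.7.2) has one PD category and treats any new lesion as PD with no confirmation step. The immune-related rule is worded as a recommendation. Section 8.3 governs continued treatment, not endpoints, and applies only to subjects without symptoms of progression who tolerate the drug and are judged to benefit. First-PD dating is also an accepted analysis for solid tumors in this same SAP, under RECIST 1.1.

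Part of this stands. The conflict lies with the response criteria in 16.7.1, not with the endpoint lines, and the stakes are low. It does not remove the point. Progression has meaning only through the response criteria, and 16.7.1 adds a rule written for this class of agent. Section 8.3 cites that appendix for lymphoma, and imaging is planned to continue until confirmation. For solid tumors the first-PD analysis sits beside a confirmed one. For lymphoma it stands alone, and Section 12 is silent.

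**Conclusion.** The SAP departs from the protocol's lymphoma progression criteria without saying so. This is explicit for PFS and DOR and is the natural reading for best response. It should be corrected or declared before the database freeze.

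The practical effect is limited, for the reasons shown under the outputs and because Hodgkin's lymphoma is the only eligible lymphoma. No magnitude can be given: the relevant quantity is the share of lymphoma subjects whose first PD is later reversed, and the documents give no figure for it.

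A reader might infer two stronger things, and the documents support neither.
- **That responses after pseudoprogression are lost.** They are not. The visit-level responses remain listed, and what changes is the derived best response and dates.
- **That one such subject moves a cohort's response rate by 1/15 = 6.7 points, with the 65% and 87% response rates in Protocol 1.4.2 making this likely.** The SAP analyses RECIL and iRECIST response separately, so that shift would need a cohort of 15 made up entirely of lymphoma subjects. The quoted rates are responses to PD-1 inhibitors in relapsed or refractory Hodgkin's lymphoma. They do not measure pseudoprogression, and Section 1.4.2 expects most subjects here to have progressed after earlier checkpoint inhibitors.

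**What to change.** In SAP 8.3.3, 8.6 and 8.9.3, add a lymphoma derivation on these lines:

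- Progression is the first PD that is confirmed by the next consecutive scan at least four weeks later, dated at that first PD.
- New-lesion measurements are included in total tumor burden, as 16.7.1 states.
- A PD followed by SD or better is disregarded, and best response, TTR, DOR and PFS continue past it.
- A PD with no later scan has its own rule, as SAP Table 5 provides for solid tumors.

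Keep the first-PD version as the second analysis, matching the RECIST 1.1 analysis for solid tumors. If the sponsor prefers first PD only, list and justify that departure in SAP Section 12, and make clear in 8.3.3 that an unconfirmed PD ends the best-response window.

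The cost is SAP wording and a small RECIL-specific derivation. The iRECIST code cannot simply be reused: RECIL time points have no unconfirmed and confirmed codes, and iRECIST keeps new-lesion measurements out of the baseline target sum (Protocol 16.6.3), whereas 16.7.1 counts them in tumor burden. No extra scans are needed, since imaging already continues until progression is confirmed. The sponsor should check that new-lesion sizes are recorded for lymphoma subjects, because the documents do not show the case report form.
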